12.1.2 Sample Size and Power Calculations

Co-Primary Objective #1: Based on current patient enrollment, we estimate a sample size of 563 patients. This has been reduced from our original estimate of 1,050 patients. We assume 23 surgeons will participate. Aim 1 has two primary endpoints: PEPI-5 self-efficacy and Active Patient Participation Behaviors (count). We desire a family-wise two-sided Type I error rate of $\alpha=0.05$; under a Bonferroni correction, tests will be conducted with nominal of $\alpha=0.05/2 = 0.025$.

Using the revised analysis model and updated accrual projections, we estimated Fisher's information for the regression parameters when the study will have complete data; inverting that information we obtained an estimate of the standard error for the intervention effect parameter, thereby computing minimally detectable Cohen's-*D* effect size for each primary endpoint at 80% and at 90% power. As a sensitivity analysis, we considered varying estimates of ICCs to ensure robust findings.

Self-Efficacy: Assuming PEPI-5 has a standard deviation (SD) of 4.3 and both within-surgeon and within-site-between surgeon ICC of 0.07, we will have 80% power to detect effects as small as $0.55*4.3=2.4$ and 90% power to detect effects as small as $0.63*4.3=2.7$ on a scale of 5-25. We consider a difference of 2 points to be clinically meaningful.

Active Patient Participation Behaviors: Assuming the active patient participation behavior count has a standard deviation of 23.1 and a within-surgeon ICC of 0.01 and within-site-between surgeon ICC of 0.0001, we have 80% power to detect a difference of $0.50*23.1=11.6$ and 90% power to detect a difference as small as $0.57*23.1=13.2$ on a 0-150 scale. We consider a difference of 10 to be clinically meaningful.

As part of the process to ascertain whether we would achieve our study goals despite the lower than planned accrual and the required revisions to the analytic plan in response to the COVID-19 pandemic, we also performed a power calculation using the estimated standard deviation for each of the two co-primary endpoints obtained from data collected during Wave 1 data (all patients are in usual care in Wave 1 and all sites had completed Wave 1). To maintain the integrity of the trial, we leveraged the ongoing collaboration with non-Alliance study statistician, [REDACTED] who is not intimately involved in the daily operations, data monitoring, and study conduct. The Alliance study statistician, [REDACTED] [REDACTED] provided [REDACTED] with the estimated standard deviations, but no granular data. The estimated standard deviations were then used by [REDACTED] to calculate the revised power to detect our a priori protocol-defined study hypotheses.

With the new analytic plan, the new projected sample size, and the revised standard deviations, we have the following updated statistical power for each of the two co-primary endpoints associated with Co-Primary Objective #1:

Self-Efficacy: Assuming PEPI-5 has a standard deviation (SD) of 3.4 and both within-surgeon and within-site-between surgeon ICC of 0.07, we will have 80% power to detect effects as small as $0.55*3.4=1.87$ and 90% power to detect effects as small as $0.63*3.4=2.14$ on a scale of 5-25. We consider a difference of 2 points to be clinically meaningful.

Active Patient Participation Behaviors: Assuming the active patient participation behavior count has a standard deviation of 19.1 and a within-surgeon ICC of 0.01 and within-site-between surgeon ICC of 0.0001, we have 80% power to detect a difference of $0.50*19.1=9.6$ and 90% power to detect a difference as small as $0.57*19.1=10.9$ on a 0-150 scale. We consider a difference of 10 to be clinically meaningful.

Co-Primary Objective #2: Mackinnon *et al.* have shown that one of the most accurate tests for mediation or indirect effect is the “asymmetric distribution of products” test¹⁰⁰ and have provided extensive simulation studies for estimating power for a variety of mediation tests.^{101,102} PowMedR software¹⁰³ was developed based on that work, which we exploit here. We assume a sample size of 563 and then deduct 23 df for surgeon effects and 7 df for number of waves; we estimate an effective sample size of 533. In addition, because we are testing two mediators, we set $\alpha=0.05/2 = 0.025$ for these two tests. Suppose we have small mediation effects with $R^2=2\%$ for the effect of the intervention on the *latent* barrier mediator (Figure 7) and for the effect of the latent mediator on PEPPi-5 score or on active patient participation behavior count. Suppose additionally that the three observed items have correlation of at least $r=0.60$. Then, the average of those three items will have reliability of $\lambda = \{r + (1/3)(1 - r)\}$, yielding net R^2 values between the intervention and the *observed* mediator and between the observed mediator and PEPPi-5 score or active patient participation behavior count of $\lambda R^2=0.82*.02=1.6\%$. Using the PowMedR software, we will have 60% power to detect mediation with small effect size and >99% power to detect mediation with medium effect size $\lambda R^2=0.82*.15=12.3\%$. Power will be higher with five items.

We will extend the period of enrollment for sites that are still recruiting within the stepped wedge design as of 8/30/2021. The extended recruitment beyond Wave 7 will continue for six sites until 12/31/2021 (see Section 12.1.3). While these additional patients will not contribute to the first co-primary objective, they will be included in the analysis for this 2nd co-primary objective; all of these additional patients will be exposed to the study intervention. We anticipate, at a minimum, that there will be 50 such patients exposed to the intervention across these six sites. We re-estimated power assuming such an increase, which leads to an increase in the power for detecting small effects from 60% to 65%.

Once mediating barriers are detected, we use a model similar to that in Aim 1 to test for an association of each barrier to a baseline indicator of socioeconomic disadvantage. We assume 30% of the sample will be disadvantaged, evenly distributed among clinics and surgeons. Assume we will be testing up to four barriers; as we desire a family-wise two-sided Type I error rate of $\alpha=0.05$, under a Bonferroni correction, tests will be conducted with nominal of $\alpha=0.05/4 = 0.0125$. Extending the same method of computing power as in Aim 1, we will have power of 80% for an effect size of 0.31 and 90% power to detect an effect size of 0.35.

We then re-estimated power assuming an additional 50 intervention patients enrolled beyond Wave 7 across six sites. As a result, the study will have 80% power to detect an effect size of 0.30 and 90% for an effect size of 0.34.

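### Bonferroni for the two primary endpoints is valid but gives up power; Holm keeps the 5% family-wise rate and gains about 3 to 5 points per endpoint if both endpoints have effects

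*Combined protocol and SAP*

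**What the plan says.** Section 12.1.2, Co-Primary Objective #1, defines the family: "Aim 1 has two primary endpoints: PEPI-5 self-efficacy and Active Patient Participation Behaviors (count"). It asks for a two-sided family-wise error rate of 0.05 and then says that "under a Bonferroni correction, tests will be conducted with nominal of" 0.05/2 = 0.025. For the sample size, "we estimate a sample size of 563 patients", reduced from 1,050.

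The same section gives detectable effects of 0.55 SD (80% power) and 0.63 SD (90%) for PEPPI-5, and 0.50 and 0.57 SD for participation. With the Wave 1 SDs of 3.4 and 19.1 these become 1.87 and 2.14 points, and 9.6 and 10.9 behaviours. The clinically meaningful differences are 2 points and 10 behaviours.

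Neither the primary analysis in Section 12.1.1 nor the power text in 12.1.2 gives a step-down, gatekeeping or alpha-recycling rule for these two endpoints. Neither requires both to be significant.

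**The concern.** A fixed split keeps each endpoint at 0.025 whatever happens to the other. Once one null hypothesis has been rejected, only one remains, and testing it at 0.05 still respects the 5% family-wise rate. Holm does this: the smaller p-value is compared with 0.025 and, if it is rejected, the other with 0.05. Control holds under any dependence between the endpoints, so the correlation, which the documents do not give, need not be known.

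This trial has little power to spare. Its sample is about 54% of the original (563/1,050). On the Wave 1 SDs the clinically meaningful differences lie between the 80% and 90% detectable effects. Enrolment cannot make up the difference, because Section 12.1.3 excludes patients enrolled after Wave 7 from the first co-primary objective.

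**Working it through.** **Inputs from Section 12.1.2.** Per-test alpha 0.025 two-sided; effects at 80% power of 0.55 and 0.50 SD; Wave 1 SDs 3.4 and 19.1; planning SDs 4.3 and 23.1; target differences 2 and 10. The correlation between the two test statistics is assumed, from 0 to 0.7.

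**Reproducing the plan.** The critical value at 0.025 two-sided is 2.2414, and 80% power adds 0.8416, together 3.0830. The implied standard errors of the effect, in SD units, are:
- PEPPI-5: 0.55/3.0830 = 0.1784
- Participation: 0.50/3.0830 = 0.1622

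Power is Φ(d/SE − 2.2414). At the stated 90% effects this gives 90.1% (d = 0.63) and 89.9% (d = 0.57), so the plan's figures reproduce. The SEs cannot be rebuilt from 563 patients, because accrual by clinic, surgeon and wave is not given.

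**Power at the clinically meaningful differences, Wave 1 SDs.**
- PEPPI-5: d = 2/3.4 = 0.588; d/SE = 3.297. Power is 85.45% at alpha 0.025 and 90.95% at 0.05.
- Participation: d = 10/19.1 = 0.524; d/SE = 3.228. Power is 83.82% at 0.025 and 89.77% at 0.05.

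**Holm, independent tests.** An endpoint gains when its p-value lies between 0.025 and 0.05 and the other endpoint is rejected at 0.025.
- PEPPI-5 gain: (90.95 − 85.45) × 0.8382 = 4.6 points
- Participation gain: (89.77 − 83.82) × 0.8545 = 5.1 points
- Both, Bonferroni: 0.8545 × 0.8382 = 71.6%
- Both, Holm: 0.9095 × 0.8382 + 0.8545 × 0.8977 − 0.7162 = 81.3%
- At least one, either method: 1 − 0.1455 × 0.1618 = 97.6%

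**With correlation** (bivariate normal; Bonferroni to Holm):

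| Correlation | PEPPI-5 | Participation | Both |
|---|---|---|---|
| 0 | 85.5% to 90.1% | 83.8% to 88.9% | 71.6% to 81.3% |
| 0.3 | 85.5% to 89.6% | 83.8% to 88.4% | 73.6% to 82.3% |
| 0.5 | 85.5% to 89.2% | 83.8% to 88.1% | 75.2% to 83.2% |
| 0.7 | 85.5% to 88.7% | 83.8% to 87.7% | 77.3% to 84.4% |

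A simulation of two million draws at correlation 0 agrees to about 0.1 point.

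**Planning SDs, independent tests.** PEPPI-5 64.3% to 70.8%; participation 66.6% to 72.7%; both 42.8% to 55.5%.

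**Only one endpoint has an effect, independent tests.** The other is rejected at 0.025 only 2.5% of the time. The gain is (90.95 − 85.45) × 0.025 = 0.14 points for PEPPI-5, or (89.77 − 83.82) × 0.025 = 0.15 points for participation. The rejection rate of the null endpoint rises from 2.5% to 2.5% × (1 + 0.8545) = 4.6%.

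**Error under the global null.** Holm makes at least one rejection exactly when Bonferroni does, so the family-wise rate is the same: 1 − 0.975² = 4.94% if independent, and at most 5% under any dependence.

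**The case against.** The strongest reply is that nothing is wrong: the plan asks for 5% family-wise control and Bonferroni delivers it. That stands. This is lost efficiency, and no inflation of error should be read into it.

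A reader might also infer that Holm adds five points to each endpoint at no cost, whatever the truth. The documents do not support that reading, for four reasons.
- The gain depends on real effects on both endpoints. Section 1.5.4 itself says that perceptions of the patient's role depend on how they are measured, so the two measures may diverge. If PEPPI-5 has its full effect and participation half its target (independent tests), PEPPI-5 gains only about 1.5 points, although participation gains about 8.
- The chance of at least one significant endpoint is unchanged. The largest gain is in the chance of both, and the plan does not make that its success criterion.
- There are small costs. The 97.5% interval for the second endpoint may include zero although Holm rejects. A truly null endpoint is also rejected more often when the other has its target effect (2.5% to about 4.6%), which is still within the family-wise limit.
- On the Wave 1 SDs, Bonferroni power at the target differences is already about 85% and 84%. The values near 65% arise only with the planning SDs.

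It is also tempting to extend the point to Co-Primary Objective #2, where the same section uses a fixed split ("because we are testing two mediators, we set" 0.025, and later 0.0125 for up to four barriers). No gain has been calculated there, and the families are not clearly delimited: two mediators are considered with two outcomes, and the barriers are selected from earlier results. The point is limited to Co-Primary Objective #1.

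Finally, the plan has already been amended during the trial, and Section 12.3.1 sends reports containing efficacy information to the DSMB every six months. A less strict rule is credible only if those choosing it have not seen comparative results.

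**Conclusion.** The point holds as a worthwhile, inexpensive gain in efficiency; the present rule is not an error. At the clinically meaningful differences with the Wave 1 SDs, Holm adds about 5 points of power per endpoint if the tests are independent and 3 to 4 points at a correlation of 0.7. Power for both endpoints rises by about 10 and 7 points respectively. With an effect on one endpoint only, almost nothing is gained and no power is lost.

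These sizes rest on the SEs implied by the plan's own detectable effects, a normal approximation and assumed correlations. That Holm never rejects less than Bonferroni, and keeps the 5% rate, rests on none of them.

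**What to change.** In Section 12.1.2, Co-Primary Objective #1, replace the Bonferroni sentence with Holm's rule: compare the smaller of the two p-values with 0.025 and, if it is rejected, the other with 0.05; if it is not, reject neither. Record the date of the change and that those making it had not seen results by intervention status.

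Keep the present power figures and label them conservative. Keep 97.5% intervals for both endpoints, with one line saying that the second endpoint's interval may include zero although Holm rejects. The cost is two or three sentences and no patients. Leave Co-Primary Objective #2 unchanged on this point.

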11.3.2 Lost to follow up

Patients will be considered lost to follow up if attempts to reach them for the follow-up survey (T2) is unsuccessful. However, patients will still have their chart review performed, unless the patient explicitly decides to withdraw from the study and withdraws consent.

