12.1.4 Missing Data

We measure our primary outcome by two methods: analysis of the audio-recording and the analysis of the follow-up survey. As patients consent immediately prior to the consultation, we anticipate that we will have minimal missingness of that component of the primary outcome. To decrease missing data from our follow-up survey, assessment burden and drop-out, we have limited the number of survey questions and provided incentives. We have included flexible means of contacting patients for the post-consultation survey, including email (primary modality), telephone, or in-person at a clinic visit. If data are missing on predictor variables of interest, data will be imputed using multiple imputation (MI) techniques (MI using chained equations).^{104,105} MI produces valid statistical estimates under missingness at random (MAR), while also accounting for additional uncertainty arising from missing data. We will perform sensitivity analyses to determine the degree to which results are sensitive to the MAR assumption. We will also account for survey non-response using an inverse probability weighting approach if we should find that there is differential survey non-response between the intervention and usual care groups according to patient characteristics that also influence the outcomes of interest.

We will consider patients as participants if they complete the audio-recording and only consider them to have dropped out if they withdraw consent. If a participant withdraws

consent, we will document: 1) the reason for dropout; 2) who decided the participant would drop out; and 3) whether the dropout involves some or all types of participation.

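### The 80% power stated for a 1.87-point PEPPI-5 difference counts all 563 enrolled women, with no stated allowance for follow-up-survey non-response

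*Combined protocol and SAP*

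**What the plan says.** Section 12.1.2 (Co-Primary Objective #1) takes its number from accrual: "Based on current patient enrollment, we estimate a sample size of 563 patients". Sections 12.1.3 and 12.4 confirm that this is an enrolment figure: 563 plus up to 62 later patients gives 625, which is the total of the planned enrolment table. The standard error comes from information "for the regression parameters when the study will have complete data".

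Two sets of PEPPI-5 figures follow, each tested at two-sided 0.025. With a standard deviation of 4.3, the detectable difference at 80% power is 2.4 points. With the Wave 1 standard deviation of 3.4, the section says "we will have 80% power to detect effects as small as" 1.87 points (0.55 × 3.4), and 2.14 points at 90% power. The clinically meaningful difference is set at 2 points.

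PEPPI-5 appears only on the survey after the consultation (Section 10.1.5). Section 11.3.2 says "Patients will be considered lost to follow up if attempts to reach them for the follow-up survey (T2) is unsuccessful". Section 12.1.4 describes steps to limit missing surveys and provides for inverse probability weighting if non-response turns out to be differential. It describes multiple imputation for predictor variables only and gives no response rate. Of the audio-recording, which yields the behaviour count, it says "we anticipate that we will have minimal missingness of that component of the primary outcome".

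**The concern.** The Wave 1 update was made to judge whether the trial could still meet its goals after slow accrual and the pandemic. For PEPPI-5 that judgement turns on 1.87 being below 2; under the standard deviation of 4.3 the detectable difference is already above the threshold. The margin is 0.13 points.

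A woman who is enrolled and recorded but never returns the T2 survey adds nothing to the PEPPI-5 comparison, yet she is among the 563. Women enrolled after Wave 7 cannot replace her, because Section 12.1.3 excludes them from this objective. If the number analysed is smaller than the number enrolled, the real detectable difference is larger than the printed one, and a modest shortfall uses up the margin on which the amendment relies.

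**Working it through.** **Inputs.** From Section 12.1.2: two-sided alpha 0.025 per endpoint; N = 563; PEPPI-5 SD 3.4, standardised effects 0.55 (80% power) and 0.63 (90%), threshold 2 points; behaviour-count SD 19.1, standardised effect 0.50 (80% power), threshold 10. The response rate r is an assumption, because the documents give none.

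**Reproducing the plan's figures.** Detectable difference = (z for 1 − 0.025/2 + z for power) × SE. The multiplier is 2.241 + 0.842 = 3.083 at 80% power and 3.523 at 90%. Scaling 0.55 by 3.523/3.083 gives 0.628, which agrees with the stated 0.63; an alpha of 0.05 would have given 0.64. The products 0.55 × 3.4 = 1.87 and 0.63 × 3.4 = 2.14 also reproduce.

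The value 0.55 itself cannot be derived exactly, because accrual by site and wave is not given. A generalised least squares information calculation of the planned model (10 clinics, 23 surgeons, six data waves per clinic, the time and restart terms, and the stated ICCs) with 563 complete records gave 0.51 to 0.57 under equal accrual and 0.51 to 0.60 under assumed unequal accrual. The stated value lies inside both ranges.

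**Effect of missing surveys on PEPPI-5.** SE at full response = 1.87/3.083 = 0.607. With response r:

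- detectable difference = 1.87/√r
- power for 2 points = Φ(2√r/0.607 − 2.241)

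| T2 response (assumed) | Detectable difference, 80% power | Power for 2 points |
|---|---|---|
| 100% | 1.87 | 85% |
| 90% | 1.97 | 81% |
| 85% | 2.03 | 79% |
| 80% | 2.09 | 76% |
| 70% | 2.24 | 70% |

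Break-even: r = (1.87/2)² = 0.874, or about 492 of 563 surveys. If 0.55 was rounded from anywhere between 0.545 and 0.555, the break-even runs from (0.545 × 3.4/2)² = 0.858 to (0.555 × 3.4/2)² = 0.890, that is, 86% to 89% response. In the least squares model the detectable difference grows slightly more slowly than 1/√r, and break-even comes at 13% to 14% missing instead of 12.6%.

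**Behaviour count.** The unrounded figure is 0.50 × 19.1 = 9.55, against 10. Break-even is (9.55/10)² = 0.912, or about 9% of recordings unusable (7% to 11% allowing for rounding of 0.50). At 5% unusable the detectable difference is 9.80, still below 10; at 10% it is 10.07.

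**Is an allowance made elsewhere?** For Co-Primary Objective #2, Section 12.1.2 starts from the same 563 and itemises its deductions: 23 degrees of freedom for surgeons and 7 for waves, leaving 533. None is for missing outcomes.

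**The case against.** The phrase about complete data is ambiguous. Beside a reference to accrual projections it may mean only that accrual has finished, and the site-by-wave inputs that would settle it are not given. A reader might infer that the sponsor demonstrably assumed zero missingness; the documents do not show that. The least squares check cannot show it either. One equal-accrual version gives 0.509 at 563 and reaches 0.550 only at 479 women, or 85% of 563. If that version were right, an allowance might already be built in; and 563 complete records would give 0.509 × 3.4 = 1.73 points, with break-even at (1.73/2)² = 75% response. But the result depends on assumed accrual and restart times, and other plausible patterns give 0.55 or more with all 563 complete. What stands is that an enrolment number is used and no allowance is stated.

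The plan also works to keep response high: email, telephone, paper, oral and in-clinic completion, up to six contacts, and an incentive. Response above 87% is possible. In addition, Section 12.1.1 adjusts for predictive patient characteristics that are absent from the displayed model. If the power calculation used that model, a cut in variance of about 3% (an assumption) would bring the detectable difference back to 2 points at 85% response, and about 8.5% would do so at 80%. Weighting for non-response, if used, could work in the other direction.

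A reader might also extend the point to the behaviour count. The documents do not support that. It comes from the recording, Section 12.1.4 expects little loss there and counts as participants those who complete the recording, and the rule that a companion's objection can leave a visit unrecorded (Section 8.2.2) gives no reason to expect 9% loss.

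**Conclusion.** The point holds for PEPPI-5. The stated 80% power at 1.87 points applies to 563 analysed surveys, whereas 563 is the number enrolled and the plan itself provides for some surveys not coming back. The margin below 2 points is gone at about 13% non-response (11% to 14% allowing for rounding).

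It would go too far to say that power is lost. The decline is gradual, from about 85% to 79% at 15% non-response and 76% at 20%, and no response rate is documented. Nor is there an arithmetic slip: every printed product reproduces, and the plan openly shows the less favourable scenario with the larger standard deviation. The sizes assume that 0.55 contains no hidden allowance, that missing surveys are spread roughly evenly over clinics and waves, and that covariate adjustment and weighting leave precision unchanged.

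**What to change.** In Section 12.1.2, say whether 563 is the number enrolled or the number expected to be analysed. Restate the PEPPI-5 detectable difference and the power at 2 points for the expected number of completed T2 surveys, using the completion rate already observed, pooled and blind to arm, with a short table over 80% to 95% response. Do the same for the behaviour count with the observed rate of usable recordings; this may simply confirm that its margin holds.

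The cost is wording and one recalculation. The stated PEPPI-5 power becomes slightly less favourable. No extra patients are needed, the analysis does not change, and pooled completion rates reveal nothing about the treatment effect.

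### The 60% (65%) mediation power treats the decision-aid-to-barrier path as 533 (583) independent patients; with Objective 1's own standard errors it is 16–20% if the model is time-adjusted and R² is raw

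*Combined protocol and SAP*

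**What the plan says.** Section 12.1.1 (Co-Primary Objective #2) tests mediation as the product of coefficient X (decision aid to barrier) and coefficient Y (barrier to engagement), in a structural equation model (SEM). The only clustering or time terms it lists are surgeon and region random effects.

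Section 12.1.2 (Co-Primary Objective #2) sets the power. It starts from 563 patients and will "deduct 23 df for surgeon effects and 7 df for number of waves; we estimate an effective sample size of 533". With alpha 0.025 for each of two mediators and a net R² of 0.82 × 0.02 on each path, it states that "we will have 60% power to detect mediation with small effect size". It adds: "Power will be higher with five items". Fifty further patients enrolled after Wave 7 give a change that "leads to an increase in the power for detecting small effects from 60% to 65" per cent; "all of these additional patients will be exposed to the study intervention".

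The same section treats two other tests differently. For Objective 1 it computes the Fisher information of the revised, time-adjusted model, and "inverting that information we obtained an estimate of the standard error for the intervention effect parameter". The detectable effects at 80% power are 0.55 SD (PEPPI-5) and 0.50 SD (participation behaviors). For the test of barriers against disadvantage it says: "We assume 30% of the sample will be disadvantaged, evenly distributed among clinics and surgeons", and "Extending the same method of computing power as in Aim 1, we will have power of 80% for an effect size of 0.31".

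**The concern.** Path X is the intervention-versus-usual-care contrast of Objective 1, in the same 563 patients and at the same alpha. In a stepped wedge, intervention status rises with wave, so time adjustment removes much of the information on the intervention. Subtracting 7 degrees of freedom does not represent that overlap. Objective 1's power calculation accounts for it and the mediation calculation does not.

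Mediation is part of a co-primary objective. Section 12.1.1 would read a significant Y with a non-significant X as meaning that the decision aid has no significant impact on the barrier. If path X has low power, a null result cannot carry that conclusion.

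**Working it through.** **Inputs (section 12.1.2).** N = 563; effective n = 533, or 583 with 50 more; alpha 0.025, taken as two-sided as in Objective 1; net R² = 0.0164 per path; detectable effects 0.55 and 0.50 SD (80% power), 0.63 and 0.57 SD (90% power). I assume a 50:50 split between periods, which the crossover schedule gives if waves are equal in size. z(0.9875) = 2.241; adding 0.842 for 80% power gives 3.083, and adding 1.282 for 90% gives 3.523.

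**1. The plan's figure.** Power per path = Φ(√(n·R²/(1−R²)) − 2.241); joint power is the product of the two paths.
- n = 533: √(533 × 0.0164/0.9836) = 2.98; per path 0.770; joint 59.3% (stated 60%).
- n = 583: 3.12; per path 0.810; joint 65.5% (stated 65%).

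Both reproduce, but only with independent-patient precision on path X: SE = 2/√533 = 0.087 SD.

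**2. Objective 1's precision for the same contrast.**

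| Endpoint | SE at 80% power | SE at 90% power | Equivalent n = 4/SE² |
|---|---|---|---|
| PEPPI-5 | 0.55/3.083 = 0.178 | 0.63/3.523 = 0.179 | 126 |
| Participation behaviors | 0.50/3.083 = 0.162 | 0.57/3.523 = 0.162 | 152 |

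That is 22–27% of 563, a loss of about three quarters.

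**3. Where the loss arises.** For the disadvantage test, alpha is 0.0125 and z = 2.498. The 80% and 90% figures give 0.31/3.339 = 0.0928 and 0.35/3.779 = 0.0926. With 30% prevalence, equivalent n = 1/(SE² × 0.3 × 0.7) = 553 and 555 of 563. By the plan's own method, a factor spread evenly over clinics and surgeons loses almost nothing. The loss on the intervention points to its overlap with wave.

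**4. Power under each reading.**

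*(a) Time-adjusted SEM, raw R².* d = 2√0.0164 = 0.256. Path Y stays at 0.770.
- SE 0.178: path X = Φ(0.256/0.178 − 2.241) = 0.210; joint 0.210 × 0.770 = 16.2%.
- SE 0.162: path X = 0.254; joint 19.6%.
- With 50 extra patients counted on path Y only (0.810): 17.0% and 20.6%.
- Five items, assuming the plan's r = 0.60 also holds for them: Spearman-Brown reliability 0.882, R² = 1.76%, d = 0.266, path X 0.226 and 0.273, path Y 0.803; joint 18.2% and 21.9%.
- Medium effect, R² = 12.3%: d = 2√(0.123/0.877) = 0.749; 97.5% and 99.1% (stated above 99%).

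*(b) Partial R² after time adjustment.* 60% stands. The implied shift is 2.98 × 0.162 = 0.48 SD to 2.98 × 0.178 = 0.53 SD, against Objective 1's whole detectable effect of 0.50–0.55 SD.

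*(c) No time terms.* About 60% stands, but path X absorbs any secular trend and the COVID restart.

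**5. Separate stepped-wedge check.** Generalized least squares with 10 clinics, 23 surgeons, 7 waves, the implementation wave dropped and 563 patients. Assumed: equal cells, mediator ICC 0 to 0.07, COVID restart waves, and the extra patients placed in two later waves at six clinics.
- Without time terms: SE 0.084–0.089; joint 56.5–60.5%.
- With time terms: SE 0.141–0.172; joint 17–26%. The 50 extra patients add 2–3 points.

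This check leans optimistic. At the plan's ICCs its SEs are 0.146–0.154 (plan 0.162) and 0.162–0.172 (plan 0.178).

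**The case against.** The strongest reply is that 60% is correct under two of the three readings, so the plan is ambiguous rather than wrong. Deducting degrees of freedom for surgeons and waves could signal a partial R², and the SEM as described has no time terms. This stands as far as it goes: 16–20% is conditional. It does not clear the plan. A partial R² makes the small effect about half an SD. Leaving out time exposes path X to the trends that Objective 1 adjusts for, and the late patients, all on intervention, add to that.

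The range also borrows endpoint SEs for a mediator whose ICC the plan does not give. That is fair; the separate check widens it to 17–26%. The interactional construct includes a scale measured once per surgeon, so its ICC could exceed 0.07.

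Smaller points stand as caveats:
- Using d = 2√R² for the medium effect gives 95–98%; the within-arm conversion used above is the better match to Cohen's d. That conversion moves the small-effect result by only about 0.3 points.
- The plan names a distribution-of-products test. Simulating it gave 57.0% and 63.7% for the plan's own case, and about 15.5–17% under reading (a).
- The disadvantage test is described as using a similar model without its time terms being listed, so step 3 is an inference. The check with and without time terms supports it.

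Finally, the consequence is bounded. The plan already admits power below 80% for small effects. Extended accrual ends on a fixed date. A barrier can still advance on coefficient Y alone, where power is about 77%.

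**Conclusion.** The concern holds, with its condition. The stated 60% and 65% give path X 3.5 to 4.2 times the information that Objective 1's calculation gives the same contrast (533/152 and 533/126). In a time-adjusted model with raw R², small-effect power is 16–20%, or 17–21% with the 50 later patients, and path X alone has 21–25%. This assumes that the mediator's clustering resembles that of the two endpoints, a 50:50 split, and path Y at n = 533 (583 with the later patients). The other two readings preserve about 60% only by enlarging the effect or by leaving path X unadjusted for time. Medium-effect power remains high. Objective 1 and the choice of interview topics are not affected; the damage is to the stated power and to the reading of null path X and indirect effects.

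**What to change.** 1. **Section 12.1.1, SEM.** Add wave, wave-squared, the post-COVID indicator and post-COVID time to both the mediator and the endpoint parts. Define wave for patients enrolled after Wave 7, since the coding stops at 7 and section 12.1.3 includes these patients in this objective.
2. **Section 12.1.2, mediation power.** State whether R² = 2% is raw or partial after time adjustment.
   - If raw, recompute path X from the Objective 1 Fisher information, over a stated range of mediator ICCs (for example 0 to 0.07, with a higher value considered for the interactional construct), for three and five items, and restate the 60% and 65%.
   - If partial, keep the figures, give the implied shift (about 0.48–0.53 SD) and drop the label small.
3. **Section 12.1.1, interpretation.** Add: *A non-significant path X or indirect effect will be reported as an estimate with its confidence interval, and not as evidence that the decision aid does not act on that barrier.*

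The cost is SAP text and one recalculation with the method already used for Objective 1 and the disadvantage test. If R² is raw, the stated power becomes less favourable. No extra patients or data are needed, and the Objective 1 analysis does not change.
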